## **14.2. Health resource utilization (HRU)**

The analysis of healthcare resource utilization/cost will be performed in HRU population based on data captured in HIS. Study scheduled visit information is not captured in the database and will not be derived. All the “visit” mentioned in this chapter refers to the information collected from database (i.e. the patient visits a hospital), instead of study scheduled visits (V1-V4).

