## 2. SCHEDULE OF ACTIVITIES (SOA)

Study participants will be followed up for 2.5 years and a total of 4 clinic visits (baseline, 6, 18, and 30 months) are scheduled for study assessments with a visit window of  $\pm 30$  days (Table 1). Baseline data will be collected at Visit 1. In addition, COPD and chronic bronchitis participants will be contacted by phone on trimonthly basis within  $\pm 7$  days of the planned date to assess the CAT and to collect information on exacerbation rates and COPD medications; healthy controls will be contacted by phone on trimonthly basis within  $\pm 7$  days of the planned date to assess the CAT only. For the 4 clinic visits (V1-V4), all the participants should be clinically stable with no exacerbation or other acute medical event for at least 30 days prior to each scheduled visit.

A subset of participants will receive additional digital and biomarker assessments during the study. If moderate/severe exacerbations are reported by the participants or detected by the investigators during the acute phase of event, the participant will be invited to site hospital for an exacerbation visit. If multiple moderate/severe exacerbations are reported or detected, the participants will be contacted in consecutive manner for an exacerbation visit. The total number of the exacerbation visits should be no more than 2, with an interval of at least 21 days. Please note, for the sub-cohort, the planned clinic visits should be scheduled with an interval of at least 60 days after a completed exacerbation visit. When any participant in the sub-cohort is implemented an exacerbation visit, then his/her next planned clinic visit (V2-V4) should be scheduled at least 60 days after completing this exacerbation visit. In this case, the participant's clinic visit may be scheduled outside of the time window of  $\pm 30$  days, which will not be considered as a Protocol Deviation (for more information please refer to the Protocol Deviation Management Plan [PDMP] for this study).

**Table 1** Time and event table

| Protocol Activity                          | Screen/Baseline |               |               |               | Study visit |   |
|--|-----------------|---------------|---------------|---------------|-------------|---|
|  | V1              | V2            | V3            | V4            | EW          | Exacerbation visit ( $\le 2$ )  |

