### **9.2.10. Healthcare Resource Utilization and Cost**

To reflect the routine medical care, the information on COPD-related healthcare resource utilization and cost occurred within site hospitals will be captured on the study questionnaire form where possible using the HIS (based on site feasibility). Information collected include:

- Unscheduled COPD outpatient visits and emergency visits
  - Number of visits, date of visit, diagnosis of visit, cost
- COPD hospitalization (including intensive care)
  - Number of hospitalization, date and length of stay, diagnosis of visit, cost
- Prescribed COPD medications
  - Medication name, date of prescription, dosage, administration, cost, whether the prescription is picked up at hospital, etc.
- Other COPD treatment, e.g. oxygen therapy, nebulizers
  - Treatment name, date, cost, etc
- Lab tests, image tests, surgeries, and other tests and procedures (e.g., spirometry, Chest X-Ray, CT)
  - Test or procedure, date of operation, cost, etc.

- Healthcare cost if feasible, e.g. general service usage, consultation fee
  - Item, date of charge
- Insurance coverage and patient out-of-pocket payment if feasible

In addition, healthcare resource utilization could occur in other places outside of the site hospitals including: (1) hospitals other than the site hospital where the subject is recruited; (2) retail pharmacy stores; (3) subjects' home. Healthcare resource utilized and associated costs will be collected using standard questionnaires at trimonthly subjects' phone interviews. Information collected include COPD-related diagnosis and treatment in the above sources:

- Outpatient visit, emergency visit, and hospitalization
  - Date, reason, length of stay (for hospitalization)
- Prescribed medications
- Over-the-counter (OTC) medications
- Other therapies, e.g. oxygen therapy, nebulizers
- Associated costs if feasible
- Lab tests, image tests, surgeries, and other tests and procedures (e.g., spirometry, Chest X-Ray, CT)

Given the high co-morbidities among COPD patients, non-COPD healthcare resource utilization will also be captured by extracting data from the HIS/EMR complimented by tri-monthly patient interviews. Information collected include:

- Non-COPD outpatient visits and emergency visits
  - Number of visits, date of visit, diagnosis of visit
- Non-COPD hospitalization (including intensive care)
  - Number of hospitalization, date and length of stay, diagnosis of visit

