## 4. ANALYSIS POPULATIONS

**Table 2. Summary of Study Populations**

Population	Definition / Criteria	Analyses Evaluated
All Screened	
The All Screened Population will consist of all participants who sign the ICF to participate in the clinical trial.
 
Participants in this population will be used for screen failure summary.
	
 
• Study Population
 

Full	The Full Population will consist of all subjects (except subject PPD ) who are enrolled in the study and attend Visit 1, and not withdraw informed consent.	
 
• Study Population
 
• Disease Progression Analyses
 
• Phenotypic Analyses
 
• Treatment Pattern and Healthcare Resource Utilization/Cost
 
• Safety Analyses
 

Sub-cohort	Sub-cohort is a subset of Full population. Subjects who are enrolled in the Biomarker & Digital sub-cohort and who provided at least one additional sub-cohort assessment.	
 
• Study Population
 
• Disease Progression Analyses
 
• Phenotypic Analyses
 
• Treatment Pattern and Healthcare Resource Utilization/Cost
 
• HRCT analysis
 

HRU	HRU is a subset of Full population. The following sites are not feasible to capture data by HIS, thus the patients enrolled from the following sites will be excluded from HRU analysis: 238160, 238222, 237965, 237971, 238155.	
 
• Treatment Pattern and Healthcare Resource Utilization/Cost
 

[figure not shown]
\*: Subject PPD cannot be categorized into either of the study arms (COPD patients, Chronic Bronchitis patients or Healthy Control), thus excluded from the Full population.

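### SAP 14.2 counts healthcare use from the enrolling hospitals' information systems only, dropping the planned off-site questionnaire source without declaring it, so counts understate total use

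*SAP*

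**What the plan says.** **Endpoint.** SAP 2.2 and Protocol 4 list, under Objective 3, counts of outpatient visits, emergency visits and hospitalisations, overall and COPD-specific, together with direct medical costs. Neither restricts these to the enrolling hospital.

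**Planned sources.** Protocol 9.2.10 says COPD-related "healthcare resource utilization and cost occurred within site hospitals will be captured on the study questionnaire form where possible using the HIS". It then recognises that "healthcare resource utilization could occur in other places outside of the site hospitals including: (1) hospitals other than the site hospital", and adds retail pharmacies and the home. For that care, "Healthcare resource utilized and associated costs will be collected using standard questionnaires at trimonthly subjects' phone interviews"; the items listed include outpatient visits, emergency visits and hospitalisations. For other conditions, "non-COPD healthcare resource utilization will also be captured by extracting data from the HIS/EMR complimented by tri-monthly patient interviews". SAP 17.5.2 repeats the questionnaire source for COPD-related use outside the site hospital.

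**Planned analysis.** SAP 14.2 states: "The analysis of healthcare resource utilization/cost will be performed in HRU population based on data captured in HIS". It defines every visit in that chapter as a contact recorded in the database, not a scheduled study visit. Visit numbers, seasonal summaries, crude rates and costs all follow from this; no output under 14.2 uses the interviews.

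**Population.** SAP Table 2 defines the HRU population as the Full population less five sites: "The following sites are not feasible to capture data by HIS, thus the patients enrolled from the following sites will be excluded from HRU analysis". SAP 2.1 declares the added population and attributes it to the state of data collection. It says nothing about a dropped source.

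**Schedule.** Protocol Table 1 places healthcare use at Visits 2 to 4, early withdrawal and exacerbation visits. It has telephone rows for CAT, exacerbations and medication but none for healthcare use. Protocol 2 describes the calls to COPD and chronic bronchitis participants as made "to assess the CAT and to collect information on exacerbation rates and COPD medications", and the calls to healthy controls as covering CAT only. Protocol 5.1 says the same.

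**The concern.** The endpoint asks how much care participants use. The analysis answers how much they use at the hospital that enrolled them. The protocol expected these to differ, which is why it planned a second source. Under SAP 14.2 an admission to another hospital contributes nothing to the hospitalisation count, and an outpatient visit elsewhere contributes nothing to the visit count.

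Two things are at stake. The tables would give a narrower quantity than Objective 3 names, with no statement in SAP 2.1 to warn the reader. The same clinical report could also treat one event in two ways. Severe exacerbations are defined partly by hospitalisation (SAP 2.2, footnote) and are ascertained by asking participants at clinic visits and three-monthly calls, with an HIS check where possible (Protocol 9.2.4, SAP 17.5.3). A COPD admission at another hospital can therefore enter the exacerbation analysis and be absent from the COPD hospitalisation count.

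**Working it through.** The documents state no expected count, rate or precision for healthcare use, so there is no figure to reproduce. The check sets the texts side by side and then works out direction and size.

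**1. Sources against use in the analysis**

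| Care | Collected from (Protocol 9.2.10) | Repeated in SAP 17.5.2 | Used in SAP 14.2 |
|---|---|---|---|
| COPD-related, at the site hospital | HIS where possible | Yes | Yes |
| COPD-related, elsewhere | Questionnaire at three-monthly calls | Yes | No |
| Non-COPD | HIS/EMR plus interviews | No | HIS only |

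The exclusion of five sites for lack of HIS capture points the same way: HIS is treated as the required source.

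**2. Effect on counts**

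Let f be the share of contacts made outside the enrolling hospital. The documents give no value, so f is an assumption, taken over 5% to 50%.

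HIS-only count = (1 − f) × total count. Adding complete off-site contacts would multiply the HIS-only count by 1/(1 − f).

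| Assumed f | HIS-only as share of total | Multiplier to reach total |
|---|---|---|
| 5% | 95% | 1.05 |
| 10% | 90% | 1.11 |
| 20% | 80% | 1.25 |
| 30% | 70% | 1.43 |
| 40% | 60% | 1.67 |
| 50% | 50% | 2.00 |

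The direction needs no assumption beyond f > 0: leaving out a non-negative component can only lower a sum. The same holds for cost totals, with f read as the off-site share of cost.

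**3. Effect on crude rates**

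SAP 14.2 divides the number of visits by the sum of (last visit date − first visit date + 1). There are two readings of those dates.

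- *Study follow-up.* The denominator does not depend on HIS contacts, so the rate falls by the share f.
- *First and last HIS contact.* This follows the chapter's own definition of a visit. The denominator is then shorter than follow-up and also depends on which contacts are recorded.

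As an illustration, let contacts follow a Poisson process at true rate λ per year over T = 2.5 years, so recorded contacts have mean m = λ(1 − f)T. Given n ≥ 1 recorded contacts, the expected span is T(n − 1)/(n + 1) plus one day; with none it is zero. The crude rate is expected contacts divided by expected span.

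| True λ per year | f | Rate, study follow-up | Rate, HIS span |
|---|---|---|---|
| 1 | 0 | 1.0 | 2.87 |
| 1 | 40% | 0.6 | 3.19 |
| 4 | 0 | 4.0 | 4.99 |
| 4 | 40% | 2.4 | 3.58 |

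On the HIS-span reading the rate is too high in three of these four rows and too low in the last (3.58 against 4). No single direction can be given for rates.

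**The case against.** Several counter-arguments carry weight.

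*The HIS basis is stated openly.* SAP 14.2 names its source and defines a visit accordingly, so a careful reader is not misled. That is fair as far as the section goes. It does not remove the mismatch with the endpoint in SAP 2.2, the conflict with SAP 17.5.2 or the silence in SAP 2.1.

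*The questionnaire data may be thin.* The schedule has no telephone row for healthcare use, the call descriptions omit it, and SAP 2.1 cites the state of data collection. A reader might infer that usable questionnaire data exist, including at the five excluded sites, and are being thrown away. The documents say only that such data were to be collected. This is why completeness has to be reported before a combined count is relied on.

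*A merged count can create bias of its own.* Calls to healthy controls cover CAT only, so off-site use could be captured in patients and missed in controls. The COPD questionnaire covers care outside the site hospital, so a questionnaire-only table for the five sites would miss care at those sites. Both points stand and limit the remedy.

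*Off-site events are not lost to the study.* Exacerbations are asked about by interview and analysed in the Full population (SAP 7.1), and off-site medication is collected by interview (Protocol 9.2.1). This is true, but it does not repair the counts in 14.2. It also means that a difference between severe exacerbations and COPD hospitalisations would not by itself measure the loss: severe events include deaths, and the two analyses use different populations.

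**Conclusion.** The concern holds for counts. As written, SAP 14.2 narrows an unrestricted endpoint to use at the enrolling hospital, contradicts the data description in SAP 17.5.2, and leaves the change undeclared in SAP 2.1. Visit and hospitalisation counts are too low by the off-site share, whatever it is: 5% to 50% low for assumed shares of 5% to 50%. Cost totals are low in the same way wherever off-site costs arose.

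Three stronger readings are not supported.

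- A reader might infer that the annual rates are low by the same share. That requires study follow-up as the denominator, which the text leaves open.
- A reader might infer that removing five sites lowers the results further. It removes participants along with their contacts; it affects representativeness and the number analysed, not the count per participant. The exclusion and its reason are declared.
- A reader might infer a distortion of known size between GOLD grades or hospital types. Unequal off-site shares could do this, but the documents give no share for any group, and SAP 14.2 plans descriptive summaries without a between-group model.

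The matter should be corrected, but it bears on a descriptive objective and not on lung function or exacerbation results.

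**What to change.** 1. In SAP 14.2, for COPD and chronic bronchitis participants in the HRU population, add a count of HIS contacts plus questionnaire-reported off-site contacts, de-duplicated on date and contact type. Show it beside the HIS-only count and report how completely the questionnaires were collected.
2. Title every HIS-only count, rate and cost *at the enrolling hospital*. Do not compare combined counts with healthy controls. State which dates define follow-up in the crude rate.
3. Declare the change of data source in SAP 2.1 and reconcile 14.2 with 17.5.2.
4. Reconcile Protocol Table 1 and the call descriptions in Protocol 2 and 5.1 with 9.2.10 on whether healthcare use is collected at the three-monthly calls.

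The cost is SAP wording, programming to merge and de-duplicate two sources, and a small schedule correction. The downside is that off-site contacts are self-reported, subject to recall and possibly incomplete, so the combined count may itself fall short. If completeness proves too poor to use, items 2 to 4 still give an honest label to what is reported.

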### **6.1. Participant Disposition**

A summary of patient disposition, including screening status, reasons for screen failures and completers of each visit will be provided for the All Screened Population. In addition, the number of participants enrolled by site will be summarized by arm using the Full population.

A summary of the number of participants in each of the analysis set described will be provided.

A summary of study disposition including factors shown in study population schematic (Figure 1 and Figure 2, respectively) will be provided for Full and Sub-cohort Population, respectively.

Duration of study will be summarized by arm in Full Population and Sub-cohort Population in a same table, using mean(sd), median, Q1, Q3, min and max. For any participants, the duration of study is defined as the number of days from enrollment to study completion or study discontinuation, i.e.

$$\text{Duration} = \text{Date of Final Visit} - \text{Date of Visit 1} + 1$$

The “Final Visit” is defined as the last scheduled visit (including exacerbation visit), regardless of Outpatient visits.

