**Table 4 Treatment Pattern Definition**

Treatment pattern	Treatment pattern Grade	Details in Treatment or the Combination
Naive	0	No any COPD treatment
Stop	0	Only COPD treatment records before 90 days from the first visit
LAMA	1	LAMA
LABA	1	LABA
ICS/LABA	2	ICS/LABA, or Combination 2, at the same time check: "ICS"+"LABA"
LAMA/LABA	2	LABA/LAMA, or Combination 2, at the same time check: "LABA"+"LAMA"
Triple(open)	3	When "Triple (open) =1": Combination 1, at the same time check: "ICS/LABA"+"LAMA", or Combination 2, at the same time check: "ICS/LABA"+"LABA/LAMA", or Combination 3, at the same time check: "ICS"+"LABA/LAMA", or Combination 4, at the same time check: "ICS"+"LABA"+"LAMA"
Triple(closed)	3	ICS/LABA/LAMA

Descriptive summary of treatment pattern for each visit will be provided with frequency and percentage for the following subgroups: gender, age (<50, 50-59, 60-69, 70-80, >80), smoking status, employment status, Type of Hospital (Type A/B), GOLD grade, Previous Exacerbation status (Yes/No), Hospitalization in preceding year (Yes/No), Presence of chronic bronchitis (Yes/No). All the concomitant medication records collected on Visit 1 within 90 days before the will be considered as baseline and the post-baseline visits contains records collected from the date of last visit to the current visit, e.g. Visit 2 refers to the record from the date of Visit 1 +1 to date of Visit 2. The descriptive summary will be provided by the treatment pattern shown in Table 4.

A shift table will be provided to show the change (step up, stable, switch, step down or stop/missing, treatment naive) of treatment patterns for each visit compared with previous visit and visit 4 compared with baseline, with number of participants in the study, number and percentage of participant in the pre-defined category. The summary will be based on all the post-baseline concomitant medication collected from the date of last visit to the current visit, e.g. Visit 2 refers to the record from the date of Visit 1 +1 to date of Visit 2, and the changes of treatment pattern are defined as:

- Step up: the treatment pattern grade become larger than previous visit ;
- Switch: the treatment pattern changed within a same grade (except grade 0)
- Stable: the treatment pattern remain the same (except grade 0)
- Step down: participants receive treatment and the grade goes down compared with the previous visit;
- Stop/missing: No treatment record in the period

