### **Endpoint: Number of Visits**

A descriptive summary of patient visits (Total, outpatient visits, emergency visits, and hospitalization) during the entire study period will be provided, both COPD related and non-COPD related visits will be presented.

A summary by season for COPD-related visits will also be provided, the definition of season is:

- Spring (Mar, Apr, May)
- Summer (Jun, Jul, Aug)
- Autumn (Sep, Oct, Nov)
- Winter (Dec, Jan, Feb)

The total follow-up period (year) and a summary of crude rate of COPD related and non-COPD related visits and the subcategory visits will be provided in a same table. The total follow-up and crude rate are defined as:

$$Total\ Followup\ Time = \sum (Last\ Visit\ Date - First\ Visit\ Date + 1)$$

$$Crude\ Rate = \frac{Sum\ of\ Number\ of\ Visits}{Total\ Followup\ Time\ (year)}$$

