**COPD-related Healthcare Resource Utilization**

Within site hospital COPD-related healthcare resource utilization and cost will be captured on the study questionnaire form where possible using the HIS (based on site feasibility). Information collected include:

- Unscheduled COPD outpatient visits and emergency visits
  - Number of visits, date of visit, diagnosis of visit, cost
- COPD hospitalization (including intensive care)
  - Number of hospitalizations, date and length of stay, diagnosis of visit, cost
- Prescribed COPD medications
  - Medication name, date of prescription, dosage, administration, cost, whether the prescription is picked up at hospital, etc.
- Other COPD treatment, e.g. oxygen therapy, nebulizers
  - Treatment name, date, cost, etc.
- Lab tests, image tests, surgeries, and other tests and procedures (e.g., spirometry, Chest X-Ray, CT)
  - Test or procedure, date of operation, cost, etc.
- Healthcare cost if feasible, e.g. general service usage, consultation fee
  - Item, date of charge
- Insurance coverage and patient out-of-pocket payment if feasible

Additionally, healthcare resource utilization could occur in other places outside of the site hospitals including: (1) hospitals other than the site hospital where the subject is recruited; (2) retail pharmacy stores; (3) subjects' home.

Outside of site hospital COPD-related healthcare resource utilization and cost will be collected using standard questionnaires at trimonthly subjects' phone interviews. Information collected include COPD-related diagnosis and treatment in the following sources:

- Outpatient visit, emergency visit, and hospitalization

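### As written, SAP 14.2 divides hospital-database visits by the time between each participant's first and last such visit, so the crude yearly rate can only be too high

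*SAP*

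**What the plan says.** SAP 14.2 bases the resource-use analysis on HIS data. Its opening paragraph says that a visit "mentioned in this chapter refers to the information collected from database (i.e. the patient visits a hospital), instead of study scheduled visits (V1-V4"). It adds: "Study scheduled visit information is not captured in the database and will not be derived".

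Under the endpoint Number of Visits, visits "during the entire study period will be provided, both COPD related and non-COPD related visits will be presented". The rate follows: "The total follow-up and crude rate are defined as"

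- Total follow-up time = sum of (last visit date − first visit date + 1)
- Crude rate = number of visits / total follow-up time in years

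SAP Table 2 removes people from the HRU population only by site ("thus the patients enrolled from the following sites will be excluded from HRU analysis"). No HIS visit is required for membership. No section gives another HRU denominator, or a rule for participants with no HIS visit or only one.

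Two other places bear on this. In SAP 6.1, "the duration of study is defined as the number of days from enrollment to study completion or study discontinuation", calculated from Visit 1 to the final scheduled visit. In SAP 14.1, part of the same chapter, visit does mean a study visit: "Visit 2 refers to the record from the date of Visit 1 +1 to date of Visit 2".

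**The concern.** Person-time should be the time during which a visit could have been recorded. Here it is the span of the recorded visits themselves. Observed time before the first and after the last HIS visit is dropped, although visits are summarised over the whole study. The people who use least care lose most of their time or all of it.

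The crude rate is the only exposure-adjusted figure in 14.2 for the visit-count endpoint of Objective 3, and Protocol 10.2.2 says counts are to be expressed per person-year. Its absolute level would be overstated by an amount that depends on how often and how regularly participants attend, so it could not be compared with rates from other cohorts.

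**Working it through.** The plan states no crude rate, so there is no figure to reproduce. The check has three parts.

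**1. Direction.** If all of a participant's HIS dates lie within the observed period, last − first + 1 cannot exceed the length of that period in days. The numerator is the same under either denominator, so the SAP rate is at least the person-time rate. The two are equal only if every participant has HIS visits on both the first and the last observed day.

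**2. A small example.** Take 30 months of 30 days (Protocol Table 1, footnote 4), so 900 days each, and four participants with 0, 1, 2 and 5 HIS visits spanning 0, 1, 31 and 801 days.

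- SAP denominator: 8 × 365.25 / (0 + 1 + 31 + 801) = 2922 / 833 = 3.51 per year
- Observed time: 8 × 365.25 / (4 × 900) = 2922 / 3600 = 0.81 per year

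**3. Size over a range of visit rates.** Follow-up T = 2.5 years (Protocol 10.1.2). The HIS visit rate, all types together, is an assumption, because the documents give none. Inflation = T / expected (last − first + 1 day).

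- Evenly spaced visits with gap g = 1/rate and random phase: expected span = T − g + 1 day. At 1 per year: 2.5 − 1 + 0.003 = 1.503, and 2.5 / 1.503 = 1.66.
- Poisson visits: given n ≥ 2 visits the expected span is T(n − 1)/(n + 1); it is 0 otherwise; add 1 day if n ≥ 1. With m = rate × T this gives T[1 − 2(1 − e^−m)/m + e^−m] + (1 − e^−m)/365.25. At 1 per year, m = 2.5: 2.5 × 0.3478 + 0.0025 = 0.872, and 2.5 / 0.872 = 2.87.
- Gamma-Poisson: the same conditional span, with rates varying between participants (shape 1 or 0.5, assumed).

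Expected denominator per participant in years, then inflation, with full follow-up:

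| HIS visits per year | Even | Poisson | Gamma-Poisson, shape 1 | Gamma-Poisson, shape 0.5 |
|---|---|---|---|---|
| 1 | 1.503; 1.66 | 0.872; 2.87 | 0.711; 3.52 | 0.623; 4.01 |
| 2 | 2.003; 1.25 | 1.526; 1.64 | 1.127; 2.22 | 0.939; 2.66 |
| 4 | 2.253; 1.11 | 2.003; 1.25 | 1.531; 1.63 | 1.256; 1.99 |
| 12 | 2.419; 1.03 | 2.336; 1.07 | 2.011; 1.24 | 1.687; 1.48 |

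With the 25% drop-out of Protocol 10.1.3, assumed uniform over the study, expected observed time is 0.75 × 2.5 + 0.25 × 1.25 = 2.1875 years. Inflation, in the same column order, is 1.76, 3.03, 3.69 and 4.18 at 1 per year; 1.13, 1.28, 1.68 and 2.04 at 4; and 1.04, 1.08, 1.26 and 1.51 at 12. With T = 900 days, the row for 1 per year becomes 1.68, 2.91, 3.56 and 4.05.

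Below one visit per year the factor climbs steeply: for Poisson visits over 900 days it is 7.0 at 0.5 per year and 31 at 0.2. Order can even reverse. A true 0.2 per year is reported as 6.2, above the 5.0 reported for a true 4 per year.

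**The case against.** **Intent.** The formula has the same shape as the duration in SAP 6.1 and Protocol 10.2.6 and is labelled follow-up time. Section 14.1 uses visit for study visits, and the statement that study visit information will not be derived could mean only that HIS records are not mapped to V2–V4. The authors may well have meant Visit 1 to final visit. This stands as doubt about intent, but it does not rescue the text: the opening paragraph of 14.2 then contradicts the formula beneath it, and a programmer following that paragraph produces the inflated rate.

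**Direction.** The bound concerns HIS-recorded visits and needs their dates to fall within the observed period, which 14.2 does not define per participant. Care outside the site hospitals is not in this numerator ("Outside of site hospital COPD-related healthcare resource utilization and cost will be collected using standard questionnaires at trimonthly" telephone interviews), so against all care used there is a separate downward error. Both limits stand. Neither corrects the denominator.

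**Impact.** The protocol endpoint is a count, the study is descriptive, and 14.2 specifies no comparison of this rate between arms. Total follow-up is printed in the same table, so a reader might see that it is short. This stands too. However, SAP 6.1 tabulates study duration for the Full and Sub-cohort Populations, not for the HRU population, so any rescaling would be approximate.

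**The remedy.** The Final Visit in SAP 6.1 can be an exacerbation visit, so for the sub-cohort it is not wholly independent of illness. The effect on person-time should be small. Linkage of eCRF dates to de-identified HIS data is not spelled out, but the HRU population is already a subset of the Full population defined by enrolling site, so HIS records must be attributable to participants.

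**Conclusion.** The denominator in SAP 14.2 is wrong as written and should be corrected before the table is produced. For HIS dates within the observed period, the crude rate of HIS-recorded visits cannot be too low and will in practice be too high. Between 1 and 12 visits per year, with full follow-up, the illustrative inflation runs from 1.03 to 4.0 times: small for frequent, regular attenders, and large where use is rare or uneven. Which end applies cannot be told from the documents, because they give neither the rate nor the pattern of HIS visits.

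The damage is confined to this one descriptive rate. Counts and costs are untouched, as are ratios between visit types if all types share one denominator. If the sponsor meant study visits, the point becomes a conflict within 14.2, which still has to be amended.

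**What to change.** Replace the denominator in SAP 14.2 with wording such as:

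> Total follow-up time (years) is the sum, over all HRU Population participants including those with no HIS visit, of (Date of Final Visit − Date of Visit 1 + 1) / 365.25, as defined in Section 6.1, with dates taken from the eCRF and merged by subject identifier. The numerator counts only HIS visits dated from Visit 1 to Final Visit inclusive. The same denominator applies to all visit types. The result is labelled as the rate of HIS-recorded visits at site hospitals; care received elsewhere is not included.

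Amend the opening paragraph of 14.2 to say that study visit dates are taken from the eCRF solely to compute person-time, and report how many HIS visits fall outside the interval. This settles the matter under either reading.

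The cost is a few sentences, one merge and a date filter, with no new data collection. There are two drawbacks. HIS use after the final scheduled visit enters neither numerator nor denominator, so a participant who attends only Visit 1 contributes one day. The rate also still understates total use where participants seek care outside the site hospitals, which is why the label matters.
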